#### **Reporting results:**

- Response rate without imputation: N, frequency and percentage of responders, SE of the response rate and 95% CI at Month 3 will be presented by treatment group.
- Response rate with imputation: N, frequency and percentage of responders, SE of the response rate at Month 3 will be presented by treatment group.
- Response rate difference with imputation: Difference between treatment groups, and corresponding SE, 95% CI and p-value at Month 3 will be presented.

#### **Figures:**

 $\circ$  Line graph of ACR50 response rate (using imputed data) with  $\pm$  SE will be plotted over time for both treatment sequences.

Note that ACR50 response rate at other timepoints will be analyzed by the same approach.

#### 6.1.1.2. Supportive Analyses

Supportive Analysis 1: The analysis of ACR50 response rate at Month 3 described in Section 6.1.1.1 will also be conducted on the PP analysis set since the FAS may include instances of non-compliance which may diminish the potential efficacy of tofacitinib. This will serve as a supportive analysis of the primary endpoint.

Endpoint: ACR50 response rate at Month 3

- Analysis time points: Month 3
- Analysis population: PP analysis set
- Method of imputation for missing data: MR=NR (specified in Section 5.3)
- Analysis methodology: Normal approximation (specified in Section 5.2.1.1)

#### **Reporting results:**

- Response rate with imputation: N, frequency and percentage of responders, SE of the response rate at Month 3 will be presented by treatment group.
- Response rate difference with imputation: Difference between treatment groups, and corresponding SE, 95% CI and p-value at Month 3 will be presented.

Supportive Analysis 2: As a supportive analysis for the ACR50 response rate at Month 3, GMMRM without imputation for missing data will be applied to the available ACR50 data collected at post-baseline visits at Week 2, Months 1, 2 and 3.

#### Endpoint: ACR50 response rate

- Analysis time points: Week 2, Months 1, 2 and 3
- Analysis population: FAS
- Method of imputation for missing data: No imputation
- Analysis methodology: GMMRM (specified in Section 5.2.1.2)

#### **Reporting results:**

- Response rate (model-based): N, frequency and percentage of responders, and SE of the response rate up to Month 3 will be presented by treatment sequence.
- Odds ratio: Odds ratio between the two treatment sequences, and corresponding 95% CI and p-value at each analysis timepoint will be presented.

Supportive Analysis 3: Another supportive analysis on the ACR50 response rate at Month 3 is performed to assess the robustness of the data to the departures from the MAR assumption. This analysis is called tipping point analysis and its methodology is briefly described in Section 5.2.1.3 and further detailed in Appendix 4.

#### Endpoint: ACR50 response rate

- Analysis time points: Week 2, Months 1, 2 and 3
- o Analysis population: FAS
- Method of imputation for missing data: Multiple imputation
- Analysis methodology: Tipping point analysis (specified in Section 5.2.1.3 and Appendix 4)

#### **Reporting results:**

- Response rate (model-based): N, frequency and percentage of responders, and SE of the response rate at Month 3 will be presented by treatment sequence, for each pair of MNAR quantities (favorable or unfavorable) applied to the probability of the ACR50 response at Month 3 for subjects with missing response in the tofacitinib 5 mg BID group and placebo group.
- Response rate difference: Difference between treatment groups, and corresponding SE, 95% CI and p-value at Month 3 will be presented, for each pair of MNAR quantities (favorable or unfavorable) applied to the probability of the ACR50

response at Month 3 for subjects with missing response in the tofacitinib 5 mg BID group and placebo group.

#### 6.2. Secondary Endpoint(s)

#### 6.2.1. Binary Endpoints

The analysis and summary methods described in this section apply to all the endpoints below.

Endpoints: ACR20 and ACR70 response rates

- o Analysis time points: All post-baseline timepoints through Month 6
- o Analysis population: FAS

Endpoint: ACR50 response rate

- Analysis time points: All post-baseline timepoints prior to and after Month 3
- Analysis population: FAS

**Endpoint:**  $\Delta$ HAQ-DI (decrease)  $\geq$  0.30 response rate

- Analysis time points: All post-baseline timepoints through Month 6
- Analysis population: Subjects in FAS with baseline HAQ-DI  $\ge 0.30$

**Endpoint:**  $\Delta$ HAQ-DI (decrease)  $\geq$  0.35 response rate

- Analysis time points: All post-baseline timepoints through Month 6
- Analysis population: Subjects in FAS with baseline HAQ-DI  $\ge 0.35$

Endpoint: PsARC response rate

- Analysis time points: All post-baseline timepoints through Month 6
- o Analysis population: FAS

**Endpoint:** PGA-PsO response (clear or almost clear and a 2-step improvement from baseline) rate

- Analysis time points: Month 1, Month 3, Month 6
- Analysis population: Subjects in FAS with baseline PGA-PsO  $\geq 2$

Endpoint: PASI75 response rate

- Analysis time points: Month 1, Month 3, Month 6
- Analysis population: Subjects in FAS with baseline  $BSA \ge 3\%$  and baseline  $PASI \ge 0$

**Endpoint:** Resolution of dactylitis (achieving DSS = 0)

- Analysis time points: Month 1, Month 3, Month 6
- Analysis population: Subjects in FAS with baseline DSS > 0

#### **Endpoint:** Resolution of enthesitis (achieving LEI = 0)

- Analysis time points: Month 1, Month 3, Month 6
- $\circ$  Analysis population: Subjects in FAS with baseline LEI > 0

## Method of imputation for missing data: MR=NR (specified in Section 5.3)

Analysis methodology: Normal approximation (specified in Section 5.2.1.1)

#### **Reporting results:**

- Response rate without imputation: N, frequency and percentage of responders, SE of the response rate, and 95% CI at each analysis timepoint will be presented by treatment group.
- Response rate with imputation: N, frequency and percentage of responders, SE of the response rate at each analysis timepoint will be presented by treatment group.
- Response rate difference with imputation: Difference between treatment groups, and corresponding SE, 95% CI and p-value at each analysis timepoint will be presented.

#### Figures:

 $\circ$  For endpoints assessed at more than 3 post-baseline timepoints, line graph of response rates (using imputed data) with  $\pm$  SE will be plotted over time for both treatment groups.

#### **6.2.2.** Continuous Endpoints

The analysis and summary methods described in this section apply to all the endpoints below.

**Endpoints:** Change from baseline ( $\Delta$ ) in ACR response criteria components (HAQ-DI, C reactive protein [CRP], Patient's Assessment of Arthritis Pain, Patient's Global Assessment of Arthritis, Physician's Global Assessment of Arthritis, swollen joint count, tender/painful joint count)

- o Analysis time points: All post-baseline timepoints
- o Analysis population: FAS

#### **Endpoint:** ΔPGA-PsO

- Analysis time points: Month 1, Month 3, Month 6
- Analysis population: Subjects in FAS with baseline PGA-PsO > 0

## **Endpoint: ADSS**

- Analysis time points: Month 1, Month 3, Month 6
- Analysis population: Subjects in FAS with baseline DSS > 0

#### **Endpoint: ALEI**

- Analysis time points: Month 1, Month 3, Month 6
- $\circ$  Analysis population: Subjects in FAS with baseline LEI > 0

#### **Endpoint:** ΔSF-36v2

- Analysis time points: Month 1, Month 3, Month 6
- o Analysis population: FAS

**Endpoint:**  $\Delta$ EQ-5D-3L and EQ-VAS

- Analysis time points: Month 1, Month 3, Month 6
- o Analysis population: FAS

#### Method of imputation for missing data: No imputation

#### Analysis methodology: MMRM (specified in Section 5.2.2)

#### **Reporting results:**

- Raw data: N, mean, s.d., SE of the mean, minimum, 1st, 2nd (median) and 3rd quartiles and maximum at baseline and post-baseline visits will be presented by treatment sequence.
- Change from baseline: N, mean, s.d., SE of the mean, minimum, 1st, 2nd (median) and 3rd quartiles and maximum will be presented for each analysis time point by treatment sequence. The LS means, SE for the LS means, and LS mean of the difference between the two treatment sequences with corresponding SE and 95% CI will be presented for each analysis timepoint.

#### **Figures:**

 $\circ$  For endpoints assessed at more than 3 post-baseline timepoints, line graph of LS mean change from baseline with  $\pm$  SE will be plotted over time for both treatment sequences.

#### **6.3. Other Endpoint(s)**

The following continuous endpoints will be analyzed and reported by methods described in Section 6.2.2.

#### **Endpoint:** ΔDAS28-3(CRP)

- o Analysis time points: All post-baseline timepoints
- Analysis population: FAS

#### **Endpoint:** ΔPGA-PsA

- Analysis time points: Month 1, Month 3, Month 6
- o Analysis population: FAS
- **Endpoint:** % in PASI and PASI clinical sign component scores
  - Analysis time points: Month 1, Month 3, Month 6
  - Analysis population: Subjects in FAS with baseline  $BSA \ge 3\%$  and baseline PASI > 0

#### **Endpoint:** % **ABSA**

- Analysis time points: Month 1, Month 3, Month 6
- $\circ$  Analysis population: Subjects in FAS with baseline BSA > 0%

#### **Endpoint: ANAPSI**

- Analysis time points: Month 1, Month 3, Month 6
- $\circ$  Analysis population: Subjects in FAS with baseline NAPSI > 0

#### **Endpoint: AWPAI-PsA**

- Analysis time points: Month 3, Month 6
- o Analysis population: FAS

#### 6.4. Subset Analyses

The primary purpose of the subgroup analyses is to check for consistency of results of the primary endpoint of ACR50 response rate at Month 3 across subgroups, i.e., make sure overall results are not being driven by some subset of subjects. There is no intention to have any specific inference within subgroups.

The subgroup comparison will be made on FAS unless stated otherwise. If sample size for a category of a subgroup factor is too small, the analysis for that subgroup may not be performed.

Endpoint: ACR50 response rate at Month 3

- Analysis time points: Month 3
- Method of imputation for missing data: MR=NR (specified in Section 5.3)
- Analysis methodology: Normal approximation (specified in Section 5.2.1.1)

#### Subgroup Analysis will be performed by:

- Gender (female, male),
- Baseline weight (< 60,  $\geq 60$  to  $\leq 100$ , > 100 kg),
- Baseline Body Mass Index (BMI) ( $< 25, \ge 25$  to  $< 30, \ge 30$  to < 40, and  $\ge 40$  kg/m^2);

- Age (< 65,  $\geq$  65 years),
- PsA disease duration (< 2 years,  $\geq$  2 years),
- Baseline PsA subtype (< 5 joints, ≥ 5 joints) formed based on counting the number of joints at baseline that are either swollen (66) or tender/painful (68), i.e., if a joint is swollen only, tender/painful only, or both swollen and tender/painful, it is only counted as one joint,

- Screening PsA subtype (arthritis mutilans: yes, no),
- Screening PsA subtype (spondylitis: yes, no),
- Baseline CRP ( $\leq 2.87, > 2.87 \text{ mg/L}$ ),
- Baseline PASI ( $\leq 20, > 20$ ) for subjects with baseline PASI > 0 and BSA  $\geq 3\%$ ,
- Baseline smoking status (never smoked, former smoker, current smoker),
- Prior bDMARD experience (bDMARD-naive vs bDMARD-experienced),
- Number of prior DMARDs-IR (1 csDMARD-IR, 2 csDMARDs-IR, ≥ 3 csDMARDs IR, ≥ 1 bDMARD-experienced). Only prior csDMARDs-IR and bDMARD use will be used to form the categories (see Appendix 3 Section 16 for prior DMARDs-IR definition). Subjects who were treated with any bDMARD or both csDMARDs-IR and bDMARDs will be counted in the "≥ 1 bDMARD-experienced" category,
- Baseline oral corticosteroid use (oral only: yes, no), Day 1 predose,
- Baseline csDMARD use (MTX only, Sulfasalazine only, Other, None), Day 1 predose.

#### **Reporting results:**

- Response rate without imputation: N, frequency and percentage of responders, SE of the response rate, and 95% CI at Month 3 will be presented by treatment group for each defined category of each subgroup.
- Response rate with imputation: N, frequency and percentage of responders, SE of the response rate at Month 3 will be presented by treatment group.
- Response rate difference with imputation: Difference between treatment groups, and corresponding SE and 95% CI (no p-value) at Month 3 will be presented for each defined category of each subgroup.

#### Figures:

• Forest plots of the differences between treatment groups (using imputed data) with corresponding 95% CI will be presented.

## 6.5. Baseline and Other Summaries and Analyses

#### 6.5.1. Baseline Summaries

Baseline characteristics will include but may not be limited to the demographic and baseline disease characteristics listed in Section 3.4.1 and Section 3.4.2 and will be summarized descriptively. For continuous variables, the summary will include N, mean, s.d. and range; for binary and categorical variables, the summary will include frequencies and percentages. A missing category will be included for those subjects with missing value. In addition to displays by treatment groups, the summaries will also be provided for both treatment groups combined.

#### 6.5.2. Prior and Baseline Treatments for Psoriatic Arthritis

Prior and baseline treatments for PsA will be characterized by the variables listed in Section 3.4.3. These variables will be summarized descriptively by frequencies and percentages for each treatment group and for both treatment groups combined.

#### 6.5.3. Concomitant DMARD Treatments

Type of concomitant DMARDs use (methotrexate, sulfasalazine, other) will be summarized by frequencies and percentages. Subjects who were treated with >1 DMARD(s) will be counted in the 'Other' category. Concomitant DMARDs use will also be summarized by counting each csDMARD regardless of other DMARD use. Frequencies and percentages will be provided for each csDMARD.

These summaries will be presented at two time points: one for Day 1 and the other for Day 1 through Month 3.

#### 6.6. Safety Summaries and Analyses

All safety data will be summarized descriptively through appropriate data tabulations, descriptive statistics, and graphical presentations. AEs, vital signs, 12-lead ECG parameters, and laboratory tests will be summarized according to the Clinical Data Interchange Standards Consortium (CDISC) and Pfizer Standards (CaPS). All the safety data analyses will be performed on the safety analysis set.

#### 6.6.1. Adverse Events

Data related to adverse events will be summarized descriptively through appropriate data tabulations, descriptive statistics, and graphical presentations:

- Incidence and severity of adverse events;
- Incidence of AEs of special interest;

- Serious infections will be summarized separately;
- Any safety events that trigger withdrawal of a subject;
- Special attention will be given to the events of anemia.

Adverse events will be reported as treatment-emergent all causality and treatment-emergent treatment-related. A treatment-emergent adverse event is any event that has: onset after the start of the first dose of study treatment, or onset prior to the first dose of study treatment and worsens in severity after the first dose of study treatment. The relationship of adverse event to study treatment is assigned by the investigator.

Adverse events will be displayed by two analysis periods: Baseline to Month 3 and Baseline to Month 6. Adverse events will be displayed from Baseline to Month 6 by treatment sequence groups and from Baseline to Month 3 by treatment groups.

In addition to the AE analyses described above, the AEs (all causality) are classified in 3 tiers and will be analyzed per the 3-tier approach. Below provides a brief summary.

Analysis of Tier-1 AEs (AEs of special interest) is covered above.

Tier-2 AEs will be analyzed per Section 5.2.3. No multiplicity adjustment will be used. Both tabular form and graphic (e.g., forest plots) display will be provided. They will be sorted by System Organ Class (SOC) and preferred terms (PT) within SOC, alphabetically, as well as by magnitude in risk ratio.

Tier-3 AEs will not be tabled separately but will be included in the standard AE analyses along with all other AEs.

It should be recognized that most studies are not designed to reliably demonstrate a causal relationship between the use of a pharmaceutical product and an adverse event or a group of adverse events. Except for select events in unique situations, studies do not employ formal adjudication procedures for the purpose of event classification. As such, safety analysis is generally considered as an exploratory analysis with the potential to generate hypotheses for further investigation. The 3-tier approach facilitates this exploratory analysis.

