## 2.1. Study Objectives

#### 2.1.1. Primary Objectives

- To compare efficacy of tofacitinib 5 mg BID versus placebo for treatment of rheumatological signs and symptoms of PsA in Chinese subjects with active PsA who have had an inadequate response to at least one csDMARD.
- To compare the safety and tolerability of tofacitinib 5 mg BID versus placebo in Chinese subjects with active PsA who have had an inadequate response in PsA to at least one csDMARD.

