#### 3.5.1. Adverse Events

An adverse event is considered treatment emergent relative to a given treatment if:

- the event occurs for the first time during the effective duration of treatment and was not seen prior to the start of treatment (for example, during the baseline or run-in period), or
- the event was seen prior to the start of treatment but increased in severity during treatment.

Any event occurring after the first day of the treatment will be attributed to the corresponding treatment period regardless whether the event occurs on- or off-treatment.

In addition to standard safety displays, a 3-tier approach will be used to summarize AEs. Under this approach, AEs are classified into 1 of 3 tiers. Different analyses will be performed for different tiers (See Section 6.6.1).

Tier-1 events: These are pre-specified events of clinical importance. The AEs of special interest (see Appendix 3 Section 13) are equivalent to Tier-1 events.

Tier-2 events: These are events that are not tier-1 but are "common". A MedDRA PT is defined as a tier-2 event if occurring in at least 4 subjects in any treatment group.

Tier-3 events: These are events that are neither tier-1 nor tier-2 events.

The 3 tiers are mutually exclusive. Tier-3 events will be included in standard safety displays and not separately displayed in specific Tier-3 tables.

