## 5.2.3. Analyses of Tier-2 Adverse Events

Number and percentage of subjects with AEs over the first 3 months will be provided for each treatment group. Tier-2 events will be analyzed using asymptotic methods proposed by Miettinen and Nurminen (1985). Risk ratios (tofacitinib 5mg BID compared to placebo) and 2-sided 95% CI will be reported. P-values will not be reported for Tier-2 events.

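### A common preferred term that is of special interest loses the risk ratio and 95% CI versus placebo that the same counts would receive in any other term

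*SAP*

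**What the plan says.** - **SAP 2.1.1 (also Protocol 2.1.1).** One of two primary objectives is: "To compare the safety and tolerability of tofacitinib 5 mg BID versus placebo in Chinese subjects".
- **SAP 3.5.1, tier definitions.** "The AEs of special interest (see Appendix 3 Section 13) are equivalent to Tier-1 events". Tier-2 takes the common events outside Tier-1: "A MedDRA PT is defined as a tier-2 event if occurring in at least 4 subjects in any treatment group". Then: "The 3 tiers are mutually exclusive".
- **SAP 5.2.3, Tier-2 only.** Events over the first 3 months are analysed by the Miettinen-Nurminen method: "Risk ratios (tofacitinib 5mg BID compared to placebo) and 2-sided 95% CI will be reported". There are no p-values. Section 6.6.1 adds tables and graphics such as forest plots.
- **SAP 6.6.1, Tier-1.** "Analysis of Tier-1 AEs (AEs of special interest) is covered above". The relevant entry in the list above that sentence is "Incidence of AEs of special interest", introduced as a descriptive summary. The same section displays adverse events by treatment group from Baseline to Month 3 and by sequence to Month 6.
- **SAP Appendix 3 Section 13.** The special-interest list has 15 entries. Some are close to ordinary reported terms (herpes zoster; anaemia, neutropenia, lymphopenia and thrombocytopenia within haematologic events). Most are adjudicated or grouped.

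**The concern.** Two preferred terms with identical counts are handled differently. The one with no special status gets an estimated contrast with an interval. The one singled out in advance as clinically important does not. This follows from a stated rule (the exclusive tiers), not from an omitted detail.

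The terms affected include risks that the Protocol itself stresses. Protocol 1.2.4.2 reports more herpes zoster with tofacitinib than with placebo in rheumatoid arthritis, a higher zoster risk in Asian than in non-Asian patients with that disease, and falls in neutrophils, lymphocytes and haemoglobin. Placebo subjects move to tofacitinib at Month 3, so Baseline to Month 3 is the only placebo-controlled safety comparison, with planned arms of 136 and 68. With so few subjects, two percentages side by side do not show how little or how much they establish.

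**Working it through.** The point is structural, so the passages come first. The documents give no precision figure for safety to reproduce; the sample size rests on ACR50 alone (Protocol 9.1).

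**Step 1: what each tier receives, Baseline to Month 3**

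| | Tier-1 (special interest) | Tier-2 (preferred term, at least 4 subjects in a group, not Tier-1) |
|---|---|---|
| Incidence by treatment group | yes (6.6.1) | yes (5.2.3, 6.6.1) |
| Risk ratio v placebo | none stated | yes (5.2.3) |
| 2-sided 95% CI for the contrast | none stated | yes (5.2.3) |
| p-value | none stated | no (5.2.3) |

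No section of either document gives Tier-1 events a risk ratio, risk difference or interval for a contrast.

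**Step 2: what the missing interval would show.** The inputs are arms of 136 (tofacitinib) and 68 (placebo) from Protocol 9.1, and event counts that are my assumptions. The Miettinen-Nurminen limits are the values of R that solve T(R) = ±1.96, where

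T(R) = (x_t/n_t − R·x_c/n_c) / √{[p_t(1−p_t)/n_t + R²·p_c(1−p_c)/n_c] · N/(N−1)}

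with N = n_t + n_c = 204 and p_t = R·p_c. Here p_c is the smaller root of N·R·p² − (R·n_t + x_t + n_c + R·x_c)·p + (x_t + x_c) = 0.

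For 6/136 v 1/68:
- Incidence: 6/136 = 4.4% and 1/68 = 1.5%.
- Risk ratio: (6/136)/(1/68) = 3.0; 95% CI 0.49 to 18.9.
- Risk difference: 4.4% − 1.5% = +2.9 points; 95% score CI −3.8 to +8.1.

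The current plan shows only the first line for a Tier-1 term. The interval would show that neither harm nor its absence is established.

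Other assumed counts, same method:

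| Tofacitinib v placebo | Risk ratio | 95% CI |
|---|---|---|
| 4 v 1 | 2.0 | 0.31 to 13.3 |
| 8 v 1 | 4.0 | 0.67 to 24.6 |
| 12 v 1 | 6.0 | 1.04 to 35.8 |
| 4 v 0 | not finite | lower limit 0.53, no finite upper limit |
| 10 v 0 | not finite | lower limit 1.35, no finite upper limit |

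At 12 v 1 and 10 v 0 the interval excludes 1. The plan would display that for an ordinary term and not for one of special interest.

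**Step 3: how often the rule bites.** A term would otherwise have been Tier-2 only if it reached 4 subjects in a group. For the 136-subject arm, P(X ≥ 4) with X ~ Binomial(136, p), by assumed 3-month incidence:

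| p | 0.5% | 1% | 2% | 3% | 5% |
|---|---|---|---|---|---|
| P(X ≥ 4) | 0.01 | 0.05 | 0.29 | 0.59 | 0.91 |

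The loss is therefore material for terms at about 2% or more. Rarer ones would mostly have been Tier-3, with no interval in any case.

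**The case against.** The strongest reply is that descriptive safety reporting is the declared plan. Protocol 9.4 and SAP 6.6 both say so, SAP 6.6.1 calls safety analysis exploratory, and SAP 5.1 makes every interval outside the primary endpoint nominal. An objective to compare safety does not by itself require an interval, and no stated conclusion becomes wrong without one. That stands, and it limits the weight of the point. It does not explain why an exploratory interval goes only to the tier without special status.

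Some of the ground is covered elsewhere. Serious infections are summarised separately, anaemia gets special attention (SAP 6.6.1), and laboratory values are tabulated by group and visit (SAP 6.6.2). None of these carries an interval for a contrast. The sponsor's reporting standards cited in SAP 6.6 might add output, but the documents do not say that they do.

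Three stronger readings are tempting, and the documents do not support them:
- **That special-interest events have no comparison with placebo at all.** Incidence is still displayed by treatment group to Month 3. What is missing is the estimated contrast and its uncertainty.
- **That all 15 listed categories lose an estimate.** Tier-2 works per preferred term. MACE, VTE, DILI and other grouped or adjudicated categories would not have had a Tier-2 estimate as categories.
- **That Tier-2 already supplies a risk difference.** Section 5.2.3 specifies risk ratios only, so a risk difference would be a new measure.

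**Conclusion.** The point holds in limited form. Under SAP 3.5.1, 5.2.3 and 6.6.1, a preferred term of special interest that occurs in 4 or more subjects in a group is denied the risk ratio and 95% CI that it would otherwise receive, and side-by-side incidence to Month 3 is all that remains. For grouped or adjudicated categories a change would add an estimate, not restore one.

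The primary efficacy conclusion is untouched. This is a cheap reporting improvement that serves a primary objective. The illustrations rest on assumed counts and incidences and on the planned arm sizes. The SAP does not list the preferred terms behind each category, so herpes zoster and anaemia are taken as terms that would otherwise qualify for Tier-2.

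**What to change.** In SAP 6.6.1, replace the sentence that refers Tier-1 analysis back to the list with a specification. For each Tier-1 category over Baseline to Month 3, by treatment group, report n (%) and the Miettinen-Nurminen risk ratio with 2-sided 95% CI as in Section 5.2.3. Label it exploratory, with no p-value and no multiplicity adjustment. Optionally add the score-method risk difference with its 95% CI, which stays finite when placebo has no events.

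Specifying this per category is better than only removing the exclusivity of the tiers, which would bring in common preferred terms but not the grouped or adjudicated categories.

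Cost: an edit to the SAP text, plus a further run of the method already planned for Tier-2 (the optional risk difference needs its own output). Downside: wide, uninformative intervals for rare events.
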